6.2.6.2 Measurements of Treatment Compliance

The by-subject listing of treatment compliance is provided for the safety analysis set, and displays results for DB and OL rimegepant treatment compliance parameters in separate columns: percentage for tablet count compliance; flags for the other parameters ("Y" or missing).

DB Treatment Compliance

The frequency table of DB treatment compliance is provided by treatment group for the DBT safety analysis set, and displays the following categories:

- DB study drug taken but not randomized
- DB tablet count compliance ≥ 80% from DB study drug start to later of last scheduled DB study drug Phase visit or DB study drug end/OL rimegepant start. Tablet count compliance is derived as 100 × actual cumulative DB tablet count/required cumulative DB tablet count, where
 - Actual cumulative DB tablet count is derived by summing the {number of days × number of tablets taken per day} across records with complete study medication start date and kit type identifier of DB rimegepant EOD/placebo EOD, DB rimegepant QD, or DB placebo QD.
 - Number of days for a record is derived as imputed study medication end date study medication start date + 1.
 - Required cumulative DB tablet count is derived as {DB maxdate DB study drug start date + 1} where
 - DB maxdate is defined as the latest of the (1) scheduled Week 2, 4, 8, and 12/EOT visit dates, and (2) DB study drug end date. Scheduled visits are identified from visit labels, and therefore exclude those containing "unscheduled" in the visit label.
 - If DB maxdate \geq OL rimegepant start date, then DB maxdate is set to OL rimegepant start date -1 day.
- > 1 DB tablet taken on any 1 day. This is determined from either of the following:
 - Records with complete study medication start date, valid DB wallet ID, and number of tablets taken per day > 1
 - Overlapping records with valid DB wallet ID (see Section 9.4)
- Incorrect DB study drug taken
 - All the time. Defined as as-treated treatment group not equal to as-randomized treatment group, i.e., any of the following:
 - Subjects randomized to rimegpant EOD/placebo EOD who took (1) ≥ 1 tablet from a DB rimegepant QD or DB placebo QD wallet, and (2) no tablets from a DB rimegepant EOD/placebo EOD wallet
 - Subjects randomized to rimegepant QD who took (1) ≥ 1 tablet from a DB rimegepant EOD/placebo EOD or DB placebo QD wallet, and (2) no tablets from a DB rimegepant QD wallet
 - Subjects randomized to placebo QD placebo who took (1) ≥ 1 tablet from a DB rimegepant QD or DB rimegepant EOD/placebo EOD wallet, and (2) no tablets from a DB placebo QD wallet.
 - At least once. Defined as any of the following:
 - Subjects randomized to rimegpant EOD/placebo EOD who took ≥ 1 tablet from a DB rimegepant QD or DB placebo QD wallet

- Subjects randomized to rimegepant QD who took ≥ 1 tablet from a DB rimegepant EOD/placebo EOD or DB placebo QD wallet
- Subjects randomized to placebo QD who took ≥ 1 tablet from a DB rimegepant QD or DB rimegepant EOD/placebo EOD wallet.
- Time on DB study drug > 14 weeks.

Results for all categories are displayed, even those with 0 counts.

OL Rimegepant Treatment Compliance

The frequency table of OL rimegepant treatment compliance is provided by treatment group and overall for the OL rimegepant safety analysis set, and displays the following categories:

- OL rimegepant tablet count compliance ≥ 80% from OL rimegepant start to later of last scheduled OLE Phase visit or OL rimegepant end. Tablet count compliance is derived as 100 × actual cumulative OL rimegepant tablet count/required cumulative OL rimegepant tablet count, where
 - Actual cumulative OL rimegepant tablet count is derived by summing the {number of days × number of tablets taken per day} across records with complete study medication start date and valid OL wallet ID.
 - Required cumulative OL rimegepant tablet count is derived as {OL maxdate OL rimegepant start date + 1} where
 - OL maxdate is defined as the latest of the (1) scheduled Week 14, 16, 20, and 24/EOT visit dates, and (2) OL rimegepant end date. Scheduled visits are identified from visit labels, and therefore exclude those containing "unscheduled" in the visit label.
- > 1 OL rimegepant tablet taken on any 1 day. This is determined from either of the following:
 - Records with complete study medication start date, valid OL wallet ID, and number of tablets taken per day > 1
 - Overlapping records with valid OL wallet ID (see Section 9.4)
- Time on OL rimegepant > 14 weeks
- OL rimegepant start on or before DB study drug end. Defined as nonmissing OL rimegepant start date ≤ DB study drug end date.
- OL rimegepant taken but DB study drug never taken. Defined as nonmissing OL rimegepant start date and missing DB study drug start date.

Results for all categories are displayed, even those with 0 counts.

eDiary Usage Compliance

The table of eDiary usage compliance is provided by treatment group for the DBT safety analysis set.

eDiary DBT usage compliance is derived as follows:

• DB study drug start to later of last scheduled DBT Phase visit or DB study drug end/OL rimegepant start: 100 × (total number of efficacy data days from the DB study drug start date to the DB maxdate)/(total number of days from the DB study drug start date to the DB maxdate), where DB maxdate is defined previously.

eDiary DBT usage compliance is summarized as a continuous variable, and in the following categories: $\geq 90\%$ compliance; $\geq 80\%$ compliance.

In addition, the number and percentage of subjects with \geq 24 days of eDiary efficacy data in the first 28 days of the OP are also displayed; see Section 7.2 for the 28-day OP analysis period and Section 9.2.2 for eDiary efficacy data days.

6.2.6.3 Nonstudy Concomitant Medications

Refer to the Core SAP for the following: definitions of select nonstudy medication types (i.e., previous, current, DBT concomitant, OL rimegepant concomitant, or follow-up); counting rules in nonstudy medication frequency tables; and nonstudy medication start and end date imputation.

The by-subject listing of nonstudy medications is provided by therapeutic class and preferred name for the enrolled analysis set. Acute migraine and prophylactic migraine medications are identified, as well as medication type.

The following conventions apply to nonstudy medications:

- Nonstudy medications are identified from those identified from the Previous Prophylactic Migraine Medications and Concomitant Medication CRFs. The Concomitant Medication CRF collects indications and links medical history and AE terms respectively to the Medical History and AE CRFs.
- Acute migraine medications are defined as nonstudy medications with either (1) an indication of "acute migraine medication" from the Concomitant Medications CRF, or (2) preferred name containing triptan, ergotamine, lasmiditan, or ubrogepant.
- Prophylactic migraine medications are defined as nonstudy medications either (1) from the Previous Prophylactic Migraine Medications CRF, or (2) with an indication of "prophylactic migraine medication" from the Concomitant Medications CRF.

Nonstudy DBT Concomitant Medications

Frequency tables of the following nonstudy DBT concomitant medications are provided by treatment group for the DBT safety analysis set: all; acute migraine. Medications are displayed in descending order of rimegepant QD frequency within therapeutic class and preferred name.

Nonstudy OL Rimegepant Concomitant Medications

Frequency tables of the following nonstudy OL rimegepant concomitant medications are provided by treatment group and overall for the OL rimegepant safety analysis set: all; acute migraine. Medications are displayed in descending order of overall frequency within therapeutic class and preferred name.

6.3 Efficacy

Efficacy endpoints are assessed by as-randomized treatment group.

Randomization is stratified using IWRS, but the randomization strata used in analyses are based on actual data, i.e., use of previous prophylactic migraine medication generally considered to have efficacy (see Sections 4.3 and 6.2.5.4). The rationale for using the actual data in analyses is that sites may erroneously report the wrong stratum in IWRS. Hence, treatment group comparisons of continuous efficacy endpoints are *adjusted* by the randomization stratum, whereas treatment group comparisons of binary efficacy endpoints are *stratified* by the randomization stratum (except in subgroup analyses). If there are sparse data within a stratum, then results may be presented unstratified.

In treatment comparisons of binary efficacy endpoints, CIs are based on a normal approximation to the binomial distribution using asymptotic standard error (ASE). Otherwise, CIs for continuous efficacy endpoints are based on the normal distribution. All CIs are 2-sided.

See Sections 7.2 and 7.3 for the definition of efficacy analysis periods and study days.

The by-subject listing of primary and key secondary efficacy endpoints is provided for the full analysis set, including the reason(s) for exclusion from the migraine analysis set: randomized more than once; not treated with study drug; treated with study drug and < 14 days of eDiary efficacy data in the OP; treated with study drug and < 14 days of eDiary efficacy data in all 3 months of the DBT Phase. Results for continuous endpoints are based on observed data that support descriptive analyses, whereas results for binary endpoints incorporate missing data imputation for risk estimation. Subjects with \ge 14 days of efficacy data (not necessarily consecutive) in the month defining the endpoint are flagged for secondary endpoints based on a single month.

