3.1.3 Exploratory Objectives

- 1. To evaluate the mean reductions from the OP in the number of migraine days per month and number of headache days per month by pain intensity (total; moderate or severe) in each month and over the entire DBT Phase for the EOD and daily rimegepant dosing regimens relative to placebo.
- 2. To evaluate the proportions of subjects with ≥ 50% reduction, ≥ 75% reduction, and 100% reduction from the OP in the number of migraine days per month and number of headache days per month by pain intensity (total; moderate or severe) in each month and over the entire DBT Phase for the EOD and daily rimegepant dosing regimens relative to placebo.
- 3. To evaluate the mean reductions from the OP in the number of migraine days per week and number of headache days per week by pain intensity (total; moderate or severe) in each week of the first 4 weeks of the DBT Phase for the EOD and daily rimegepant dosing regimens relative to placebo.
- 4. To evaluate the proportions of subjects with ≥ 50% reduction from the OP in the number of migraine days per week and number of headache days per week by pain intensity (total; moderate or severe) in each week of the first 4 weeks of the DBT Phase for the EOD and daily rimegepant dosing regimens relative to placebo.
- 5. To evaluate the proportions of subjects with a migraine day and headache day by pain intensity (total; moderate or severe) on each day of the first week of the DBT Phase for the EOD and daily rimegepant dosing regimens relative to placebo.
- 6. To evaluate the mean number of acute migraine-specific medication days per month in each month and over the entire DBT Phase for the EOD and daily rimegepant dosing regimens relative to placebo.
- 7. To evaluate the mean number of acute migraine medication days per month in each month and over the entire DBT Phase for the EOD and daily rimegepant dosing regimens relative to placebo.
- 8. To evaluate the frequency of liver function test (LFT) elevations (AST, ALT, or TBL) based on fold changes above ULN in subjects treated with rimegepant during the DBT and OLE Phases.

- 9. To evaluate the frequency of ALT or AST > 3x ULN in temporal association with nausea, vomiting, anorexia, abdominal pain or fatigue in subjects treated with rimegepant during the DBT and OLE Phases.
- 10. To evaluate the mean changes from baseline in MSQ domain scores during the DBT and OLE Phases.

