5 SAMPLE SIZE, POWER, AND TYPE 1 ERROR

The study randomizes approximately 220 subjects per arm. Based on data from study C4951025 (BHV3000-305), we estimate that this results in roughly 200 subjects per arm in the migraine analysis set. Assuming rimegepant provides roughly a 1.1-day advantage over placebo on the primary endpoint, a common standard deviation (SD) of 3.5 days, and a 2-sided alpha level of 0.025, then the study has roughly 80% power on the primary endpoint.

In study C4951025 (BHV3000-305), rimegepant provided a 0.8-day advantage over placebo. With daily dosing, we expect the treatment effect to increase. Using the data from study BHV3000-305, the SD of the primary endpoint was estimated to be roughly 3.5 days.

Type 1 error is controlled using a 2-sided alpha level of 0.025 and hierarchical testing. The significance of the primary endpoint is evaluated at a 2-sided alpha level of 0.025 for each rimegepant dosing regimen versus placebo. If the primary endpoint is significant for a rimegepant dosing regimen, then the secondary efficacy and outcomes research endpoints are tested hierarchically, each at a 2-sided alpha level of 0.025, in the order specified in Section

3.2.2. Thus, for a rimegepant dosing regimen, a secondary efficacy or outcomes research endpoint is tested only if the preceding secondary endpoint in the hierarchy is determined to be significant (i.e., p-value ≤ 0.025). If a test in the hierarchy is not significant, then any further tests on endpoints in the sequence have p-values presented only for descriptive purposes, and no conclusions are drawn from those results. Note that secondary safety endpoints are not tested.

For exploratory endpoints, no attempt is made to adjust for multiplicity. Any exploratory endpoints for which p-values are produced are evaluated at an unadjusted, 2-sided alpha level of 0.025 and presented only for descriptive purposes.

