6.3.2 Secondary Efficacy Endpoints

6.3.2.1 Percentages of Subjects With Reduction From OP in Number of Migraine Days per Month Over Time on DBT

Analyses are based on the migraine analysis set with eDiary efficacy data dates in the OP and on-DBT efficacy analysis periods (see Section 7.2).

In analyses by months, subjects must (1) achieve the reduction criterion from OP in the number of migraine days per month in the specified month, (2) have \geq 14 days of eDiary efficacy data (not necessarily consecutive) in the specified month, and (3) have \geq 1 migraine day (absolute not prorated) of appropriate pain intensity in the OP analysis period to be classified as responders in the specified month. Otherwise, subjects are classified as failures in the specified month.

In analyses of the overall DBT, subjects must (1) achieve the reduction criterion from OP in the number of migraine days in the overall DBT, and (2) have ≥ 1 migraine day (absolute not prorated) of appropriate pain intensity in the OP analysis period to be classified as responders. Otherwise, subjects are classified as failures.

Treatment Group Comparisons

For each pain intensity (total; moderate or severe) and select percentage reduction ($\geq 50\%$, \geq 75%, and 100%), the percentages of subjects with reductions in the number of migraine days per month are compared between each rimegepant treatment group and placebo using Mantel-Haenszel risk estimation with stratification by randomization stratum (yes, no). Percentages are calculated against the number of subjects in the migraine analysis set.

The table displays the following statistics at each month of the DBT Phase and overall DBT by pain intensity:

- Response rate (i.e., "n/N" and percentage), ASE, and 97.5% CI for each treatment group
- Stratified percentage difference between each rimegepant treatment group and placebo (rimegepant_i placebo; i = 1 and 2), ASE, 97.5% CI, and p-value
- Response rate (i.e., "n/N" and percentage), ASE, and 97.5% CI by randomization stratum for each treatment group
- Percentage difference between each rimegepant treatment group and placebo (rimegepant_i placebo; i = 1 and 2), ASE, 97.5% CI, and p-value by randomization stratum.

Results for the endpoint of \geq 50% reduction of moderate or severe pain intensity in the overall DBT support secondary objective #1. Results for all other endpoints support exploratory objective #2.

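### The normal-approximation intervals set for binary efficacy endpoints fail where responders are few, chiefly in the exploratory 100%-reduction rows; use score intervals in the exploratory and by-stratum rows

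*SAP*

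**What the plan says.** SAP 6.3 gives the rule for every binary efficacy endpoint: "In treatment comparisons of binary efficacy endpoints, CIs are based on a normal approximation to the binomial distribution using asymptotic standard error (ASE". This is the Wald form, estimate plus or minus z times the ASE. The same section adds "All CIs are 2-sided", and the tables use the 97.5% level.

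SAP 6.3.2.1, under its treatment-comparison heading, asks for the response rate, ASE and interval in each arm, the stratified difference with interval and p-value, and the same quantities within each stratum ("ASE, and 97.5% CI by randomization stratum for each treatment group"). It does so for reductions of at least 50%, at least 75% and 100%, for two pain-intensity definitions, at each month and over the whole double-blind phase. SAP 6.3.3.2 repeats this for headache days. The 100% rows serve exploratory objective 2 in SAP 3.1.3, which covers "100% reduction from the OP in the number of migraine days per month and number of headache days per month by pain intensity".

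The only provision for thin data is in SAP 6.3: "If there are sparse data within a stratum, then results may be presented unstratified". Neither document gives an exact or score interval, or a rule for zero cells. Under SAP 5, exploratory p-values are "evaluated at an unadjusted, 2-sided alpha level of 0.025 and presented only for descriptive purposes".

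**The concern.** A Wald interval takes its width from the observed proportion. If an arm or stratum has no responders, the estimated standard error is zero and the interval has no width. The table then shows certainty where there is least information. With a few responders the interval extends below 0%.

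Complete absence of migraine or headache days is where low counts are most plausible. Protocol 5.2 requires at least 4 migraine days in the 28-day Observation Phase, and all must disappear. The stratum with no prior prophylactic use is capped at 30% of randomized subjects (Protocol 1.5.1), so its rows rest on about 60 subjects per arm. The sparse-data clause does not repair this: dropping stratification keeps the same interval formula, and the by-stratum rows are already unstratified.

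At stake is the honesty of the error bars in these descriptive rows. For 100% reduction alone there are 2 event types × 2 intensities × 4 time points × 3 arms = 48 per-arm intervals, and twice that, 96, by stratum.

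**Working it through.** **Inputs.** About 200 subjects per arm in the migraine analysis set (SAP 5). Smaller stratum at most 30% (Protocol 1.5.1): 0.30 × 200 = 60 per arm. Two-sided 97.5% intervals, so z = 2.2414 and z² = 5.024. Response rates are assumptions, because neither document gives any for a binary endpoint.

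**The plan's own figure.** The only stated design figure is roughly 80% power on the primary endpoint. The standard error of the difference is 3.5 × √(2/200) = 0.35, and 1.1/0.35 = 3.143. Power is Φ(3.143 − 2.241) = 81.6%, which agrees and confirms n and z.

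**Zero responders.** Wald: 0 ± 2.2414 × √(0 × 1/n) = 0% to 0% at any n. The Wilson upper limit is z²/(n + z²): 5.024/65.024 = 7.73% for n = 60 and 5.024/205.024 = 2.45% for n = 200. Clopper-Pearson gives 7.04% and 2.17%. For 0 versus 0, the Wald difference interval is 0 to 0 and the test statistic is 0/0. Newcombe gives ±7.73 points (60 per arm) or ±2.45 points (200 per arm).

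**One to four responders.** The Wald lower limit is negative when the count x is less than z²(1 − x/n). At x = 4 the right side is 4.69 (n = 60) or 4.92 (n = 200), so the limit is below zero; at x = 5 it is not. For 1/60, Wald gives −2.04% to 5.37% and Wilson 0.24% to 10.56%.

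**Single-arm coverage**, by summing exact binomial probabilities over the counts whose interval contains the true rate (nominal 97.5%):

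| True rate (assumed) | Wald, n = 200 | Wilson, n = 200 | Wald, n = 60 | Wilson, n = 60 | Chance of 0%–0% at n = 200 / n = 60 |
|---|---|---|---|---|---|
| 1% | 86.6% | 98.4% | 45.3% | 97.8% | 13.4% / 54.7% |
| 2% | 91.0% | 98.0% | 70.2% | 96.8% | 1.8% / 29.8% |
| 5% | 93.5% | 96.7% | 95.3% | 97.0% | about 0 / 4.6% |
| 10% | 96.3% | 97.6% | 94.5% | 98.4% | about 0 / 0.2% |
| 40% | 97.0% | 97.5% | 96.5% | 97.6% | about 0 / about 0 |
| 50% | 97.2% | 97.2% | 97.3% | 97.3% | about 0 / about 0 |

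At n = 60 and 1%, the shortfall is almost exactly the chance of no responders: 100% − 54.7% = 45.3%.

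**Coverage for differences** (unstratified):

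| Rates | Per arm | Wald | Newcombe |
|---|---|---|---|
| 2% v 1% | 60 | 83.6% | 99.98% |
| 1% v 1% | 60 | 99.96% | about 100% |
| 3% v 1% | 200 | 96.5% | 99.2% |
| 1% v 1% | 200 | 98.6% | 99.9% |
| 50% v 40% | 60 | 97.2% | 97.6% |
| 50% v 40% | 200 | 97.4% | 97.6% |

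So Wald can under-cover when low rates differ and over-covers when they are equal and very low.

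**The case against.** The strongest reply is that little depends on these rows. They are exploratory or subgroup rows, their p-values are descriptive, and each per-arm row prints the count beside the interval, so a reader sees 0/60 next to 0% to 0%. This stands, and it limits the severity.

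The second reply is that rarity is not shown. No rate is given, and some rules make 100% reduction easier: the moderate-or-severe rows need only one such day in the Observation Phase, and a month counts with 14 diary days. This also stands. A zero-width interval is unlikely from about 3% upward at n = 200 (0.2%) and from about 10% at n = 60 (0.2%). The low coverages apply only to low rates.

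The third is that the Core SAP or the mock tables, which are not available here, may hold a zero-cell convention. That is possible, but SAP 6.3 states the interval method outright and does not refer elsewhere for it.

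A reader might infer three stronger points that the material does not support:

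- **That Wald p-values are too liberal.** For 5/200 versus 0/200, Wald gives p = 0.0235 and Fisher's exact test 0.061. But the pooled score test gives z = 2.250, p = 0.0244, so the gap reflects Fisher's conservatism. Under equal rates, the Wald rejection rate at nominal 2.5% is 1.4%, 2.3%, 2.6% and 2.6% (n = 200) and 0.04%, 0.4%, 2.1% and 2.8% (n = 60) at true rates of 1%, 2%, 5% and 10%.
- **That every by-stratum row is unreliable.** At 40% to 50% response with 60 subjects, single-arm coverage is 96.5% to 97.3%.
- **That all binary intervals are covered.** The sentence concerns efficacy; the liver-test intervals in SAP 6.4.2.2 do not fall under it.

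**Conclusion.** The point holds as a minor one. The zero-width interval, the negative lower limit at 1 to 4 responders and the undefined 0 versus 0 p-value follow from the stated formula and need no assumption beyond a low count.

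How often they occur, and the loss of coverage (to 87–91% at n = 200 and 45–70% at n = 60), rest on assumed true rates of 1% to 2% and on the smaller stratum being at its 30% cap. For differences the error has no single direction.

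The primary endpoint is not involved. The alpha-tested endpoint, at least 50% reduction in moderate or severe migraine days over 12 weeks, is not affected at mid-range response rates, where coverage is about 97%. No conclusion in the testing hierarchy changes.

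**What to change.** In SAP 6.3, limit the ASE-based interval to the alpha-tested endpoint of at least 50% reduction in moderate or severe migraine days over the whole double-blind phase. Keep that endpoint's Mantel-Haenszel difference, interval and p-value, so that its interval and test stay consistent.

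For the exploratory and by-stratum binary efficacy rows, specify Wilson score intervals for per-arm response rates and Newcombe or Miettinen-Nurminen intervals for differences, with a stratified version where the difference is stratified. State that no p-value is shown when neither arm has a responder.

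The cost is a short SAP edit and a programming option. Intervals for rare outcomes become wider, Newcombe intervals are conservative at very low rates (close to 100% coverage in several cells above), and one table will carry two interval methods, which needs a footnote.
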